disenrolled from employer-sponsored plans after February 2020 will be identified, and those aged 4-64 with an ICD-10 diagnosis code for asthma in claims data after January 1, 2019 will be contacted by email and invited to participate. Recruitment materials will include a description of the study and a RedCap survey link which will ask screening questions to determine eligibility. Any participant suspected of being duplicative or fraudulent will be ineligible for the study and removed. We will collect information on race/ethnicity and select a sample representative of the racial/ethnic distribution of patients with asthma, with no more than 60% non-Hispanic White selected for the sample (PC-2). The estimated racial/ethnic and gender of the study population is described in Table 1.

Race	Male (N)	Female (N)	Total (N)				
American Indian/Alaska Native	0	0	0				
Asian	0	0	0				
Black/African American	19	96	115				
Hawaiian/Pacific Islander	0	0	0				
White	76	201	277				
Multirace	19	19	38				
Ethnicity	Male (N)	Female (N)	Total (N)				
Hispanic (Latino/Latina)	10	19	29				
Non-Hispanic	104	297	401				

Table 1. Estimated Racial/Ethnic and Gender Enrollment

Design

We will conduct a pilot randomized controlled trial where we will randomize participants who lost coverage to: 1) be offered a combination of automated chat bot and personalized outreach provided by AAFA-affiliated navigators (n=145), or 2) be a wait-list control (n=285). We will use a wait-list, usual care control group as the comparator given that there is no other standard treatment or practice for people with asthma who lose insurance coverage to which to compare our navigation intervention (RQ-5). A diagram of the study flow can be found in Figure 1. After randomization, participants will be given a RedCap link for a baseline survey. REDCap is a HIPAA secure web-application that the Harvard Pilgrim IRB has approved for securely collecting survey data via email which allows study subjects to enter data directly into a form that is then transmitted securely to the Harvard Pilgrim server. The survey instrument will contain structured, closed-ended questions designed to be completed in an average of 20 minutes. The survey will assess past and current insurance coverage, asthma severity and control, medication use and adherence, other asthma care use, current access and cost challenges, and COVID-19 related illness. We will offer a \$20 gift card for completion of the survey.

Intervention

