Four months later, intervention and control subjects will be emailed a RedCap link to a similar followup survey to measure changes in insurance coverage, asthma care and control, health care access, and affordability. The survey will be designed to be completed in an average of 20 minutes and we will offer a \$20 gift card for completion. We will attempt to contact non-responders by telephone to encourage them to complete the surveys (MD-1). Survey subjects will be asked for permission to be contacted again for participation in a telephone interview for Aim 2.

Outcomes

Outcomes include patient-centered, patient-reported outcomes that people with asthma have raised as concerns in our prior qualitative work in the parent project and that have been identified as meaningful in the parent AFFORD project by our stakeholder partners from AAFA, the Patient Family Advisory Council, and the AFFORD Advisory Board (RQ-6, PC-1, PC-3). The primary outcome will be whether the participant with asthma (or their child with asthma) has insurance coverage. Secondary outcomes will include whether the person with asthma used less asthma medication than prescribed because of cost, and whether they experienced health care-related financial burden (problems paying medical bills and/or paying off medical bills over time, having to set up a payment plan with a doctor or hospital, having trouble paying for other basic bills like food, heat, or rent because of medical costs). Other outcomes will assess asthma care use, asthma control using the Asthma Control Test (ACT), health status, mental health/worry, and material hardships such as food or housing insecurity. These include validated measures and measures used in prior surveys by the study team and others (IR-4).²⁶⁻³³

Analysis Plan (IR-3)

We hypothesize that participants receiving the intervention will be more likely to have coverage at four-month follow up (primary outcome) and will be less likely to report non-adherence to asthma medications, delayed/forgone asthma care, and financial burden than those receiving usual care (secondary outcomes).

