We will compare unadjusted outcomes between the intervention and control groups using chi square and t tests; because of the randomized study design this difference measures the causal impact of the intervention. We will conduct post hoc exploratory analysis to assess differences in intervention effectiveness by race/ethnicity to assess whether the intervention reduces racial/ethnic coverage disparities (RQ-4; HT-1). Given the small pilot nature of this study, these analyses will be hypothesisgenerating rather than hypothesis-testing (HT-2-4). The survey will measure important co-variates such as age, gender, income, race/ethnicity, education, state of residence, asthma severity, and family composition, and analyses will adjust for any co-variates that are not balanced between study groups (IR-1). In this pilot study, efficacy testing will be limited but we expect to have 100 intervention and 200 control subjects with follow-up data to be able to detect absolute differences of 10% or more between study groups in changes in uninsurance rates with 80% power with a two-tailed alpha of 0.05. We assume 30% loss to follow-up from baseline to four-month follow-up. Given the small pilot nature of this study, we will track dropout carefully in order to inform feasibility assessment and planning for a larger trial. We will closely monitor timing of dropout, impact of strategies such as telephone outreach, and characteristics of those dropping out compared to those retained, and will use multiple imputation methods to conduct a sensitivity analysis to test the sensitivity of findings analyzed with and without imputed data (MD-2-5). Findings will be reported using CONSORT reporting guidelines (IR-6).

Patient stakeholders from the AFFORD Patient Family Advisory Council will provide input on interpretation of study findings in the context of their lived experience, and will provide input on strategies for dissemination to key stakeholders (PC-1, PC-4).

Aim 2:

Overview

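### The non-responder call is described as a prompt to finish the 20-minute web survey, with no provision for recording four-month coverage, the primary outcome, on the call itself

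*Combined protocol and SAP*

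**What the plan says.** The primary outcome is defined in Aim 1, Outcomes: "The primary outcome will be whether the participant with asthma (or their child with asthma) has insurance coverage". The hypothesis at the start of the Analysis Plan places it in time: "participants receiving the intervention will be more likely to have coverage at four-month follow up (primary outcome".

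The four-month data come by web form. Under Data collection, "Four months later, intervention and control subjects will be emailed a RedCap link", and "The survey will be designed to be completed in an average of 20 minutes", with a $20 gift card for completion. For people who do not respond, the procedure is "We will attempt to contact non-responders by telephone to encourage them to complete the surveys (MD-1". No section describes a short form, completion by telephone, a coverage question on the call, or another source of coverage status.

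On attrition, the Analysis Plan states "We assume 30% loss to follow-up from baseline to four-month follow-up" and "we expect to have 100 intervention and 200 control subjects with follow-up data". It also tracks the timing of dropout and the effect of telephone outreach, compares people lost with people retained, and uses multiple imputation as a sensitivity analysis.

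**The concern.** The calls are already planned, so the study will be speaking to some people who have stopped responding. The outcome that matters most is far shorter than the instrument they are asked to return to. If the call yields only a reminder, anyone who picks up but does not then do the survey adds nothing to the primary comparison.

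The Analysis Plan treats the unadjusted difference as causal because of randomisation. That protection covers everyone randomised; it does not automatically cover the roughly 70% who return a survey. Motives to respond may also differ by arm: under the Aim 1 Overview, controls are offered the chat bot after they complete the follow-up surveys, whereas intervention participants already have it. Dropout tracking and imputation describe or model the loss, but neither observes a non-responder's four-month coverage.

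**Working it through.** **Inputs.** Randomised: "navigators (n=145), or 2) be a wait-list control (n=285", 430 in all (Aim 1, Design). Expected with follow-up: 100 and 200. Loss: 30%. Target difference: 10 percentage points, two-sided alpha 0.05 (Analysis Plan). Not given: the telephone contact rate, the willingness to answer one question, and the uninsured rate in either arm.

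**The plan's own figure.** 145 × 0.70 = 101.5 and 285 × 0.70 = 199.5, which agrees with the stated 100 and 200.

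**Expected missing.** (145 − 100) + (285 − 200) = 45 + 85 = 130, and 130/430 = 30.2%.

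**Effect of asking on the call.** Let f be the share of the 130 who are both reached and willing to answer; f is an assumption. Outcomes gained = 130f. If recovery is similar in the two arms, the standard error scales by about √[300/(300 + 130f)].

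| f (assumed) | Gained | Still missing | Standard-error ratio |
|---|---|---|---|
| 0 | 0 | 130/430 = 30.2% | 1 |
| 10% | 13 | 117/430 = 27.2% | √(300/313) = 0.98 |
| 25% | 32.5 | 97.5/430 = 22.7% | √(300/332.5) = 0.95 |
| 50% | 65 | 65/430 = 15.1% | √(300/365) = 0.91 |

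**What f stands for.** It is a product of two unknown rates. For illustration, 40% reached × 30% answering = 12%, and 50% × 50% = 25%. Reaching f = 50% needs both rates near 71% (0.71 × 0.71 = 0.50), so the last row is optimistic.

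**Room for attrition bias.** With a fraction m missing in each arm, the gap between the best-case and worst-case risk difference is 2m. At m = 30%, 27%, 22.5% and 15% this is 60, 54, 45 and 30 points, against a target of 10. More moderately, the bias of the observed difference is m × (effect in those observed − effect in those missing). If those effects were 10 and 0 points (an assumption), the bias is 0.30 × 10 = 3 points, so the effect in everyone randomised would be 7. The same gap at m = 15% gives 1.5 points.

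**Power.** Using Φ[(0.10 − 1.96·SE₀)/SE₁], with SE₀ pooled and SE₁ unpooled, 101.5 and 199.5 participants, and an assumed 20% versus 10% uninsured: SE₀ = 0.0454, SE₁ = 0.0411, power 0.61. At f = 10%, 25% and 50% it becomes 0.63, 0.65 and 0.70. At an assumed control rate of 15% the series, from f = 0, is 0.76, 0.78, 0.81, 0.84; at 30% it is 0.46, 0.47, 0.50, 0.54.

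**The case against.** The strongest objection is that the gap is read from silence. A reader might infer that calls are made only as reminders, that telephone completion is ruled out, or that a person reached by telephone is formally counted as lost. The documents say none of this: they give one purpose for the call, do not bar other uses, and do not define loss in those terms. Nor do they give the number of coverage items, so the claim that one question of under a minute would suffice is a reasonable guess, not a fact. What stands is narrower: the procedure as described makes no provision for recording coverage on the call.

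A reader might also infer that most of the 130 are recoverable. The documents do not support that. The 30% may already be net of the planned calls, in which case the 130 consist of people never reached and people who still decline. A telephone number may not be held for everyone: recruitment through the health plan is described by email, and Aim 2, Participants, asks interview candidates for an email and/or phone number. This is why the low case matters.

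Two further objections stand. Coverage is also asked at baseline and one month, so imputation can draw on a lost participant's own earlier answers and need not borrow solely from responders. And a web-only repeat changes both the mode and the people analysed, so it cannot isolate a mode effect.

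It is also fair that this is a pilot that describes its efficacy testing as limited and already monitors dropout. That limits the weight of the point. It does not remove it, because information on retention for a larger trial is among the pilot's purposes.

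**Conclusion.** The point holds as a low-cost improvement to data collection; it is not an error or contradiction in the plan. As described, a person reached on the four-month call who does not then complete the web survey would contribute no primary outcome, and 130 of 430 are expected to lack one.

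The size of the benefit rests on an assumed recovery share, taken as similar in both arms. At 10%, 25% or 50%, missingness falls from 30% to about 27%, 23% or 15%, and the standard error by about 2%, 5% or 9%. Precision and power improve modestly. The better reason to act is the smaller scope for attrition bias, together with some observed outcomes among reachable non-responders. Those answers would not speak for people never reached, and the documents give no direction for any bias.

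**What to change.** Amend Aim 1, Data collection, as follows for the four-month non-responder call:

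- If the person declines the web survey, the caller asks the current-coverage item in the survey's own wording. Asking it only after a refusal keeps the full survey as the first request.
- Use the same script, number of attempts and time window in both arms. Callers should be study-team staff and not AAFA navigators, who may also telephone intervention participants.
- Record the mode of collection for each answer.

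In the Analysis Plan, include the telephone answers in the primary analysis, repeat the analysis on web responses only as a sensitivity analysis, and report loss of the primary outcome separately from loss of the full survey, by arm. If telephone completion is already intended, say so and add the same safeguards.

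The cost is a short script on calls already planned and IRB wording. The downside is mixed-mode collection. The web-only repeat shows how far the result depends on the telephone answers; it should not be presented as separating a mode effect from a real difference between responders and non-responders.

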In this aim, we will conduct a pilot randomized controlled trial of patients with asthma or parents of children with asthma who lost employer-sponsored coverage during the COVID-19 pandemic. Potential study subjects will be recruited through AAFA and HPHC. Eligible participants will be randomized into one of two study groups: 1) an intervention group that receives access to an asthma chat bot and personalized insurance navigation (n=145), or 2) a wait-list control group (n=285). At study entry, participants will receive an online baseline survey to assess outcomes related to insurance coverage, asthma severity and control, medication use and adherence, asthma care access and affordability, and COVID-19 related illness. The intervention group will be offered the chat bot and AAFA navigation services. Navigation will be provided through AAFA's existing online patient community platform that provides assistance with clinical, educational and financial questions and includes secure, personal messaging capabilities that will be supplemented with telephonic outreach. One month later, we will field a follow-up survey to measure short-term changes in outcomes; for the intervention group, this survey will also measure implementation outcomes including uptake, feasibility, acceptability, and usability. Four months later, we will field a second follow-up survey to measure longer-term changes in outcomes. Control subjects will be offered the chat bot after completion of the follow-up surveys. If findings suggest that the intervention is feasible and effective, we will use effect sizes from this pilot to power a larger comparative effectiveness trial in the future.

Participants

Eligible subjects will include adults aged 18-64 years who have asthma or have a child with asthma aged 4-17 years, and lost employer-sponsored health insurance after February 2020. Only one person per household will be eligible. Potential subjects will be recruited through AAFA, who will send out a description of the study to potential subjects through its online community, email listserv, website, Facebook page, and newsletter, and through its partner hospital programs and Medical Scientific Council (PC-2). Potential subjects will also be recruited through HPHC. Members who

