After completion of the baseline survey, intervention subjects will be sent an email with information about AAFA's asthma chat bot and a link to access it and information about AAFA's insurance navigation program, how it can help with finding coverage and managing asthma costs, and how to access it via group and private messaging within AAFA's asthma community platform with the availability of telephonic follow-up from AAFA navigators. Subjects can access AAFA's community

platform through a password-protected account, through which they can join the private group where they can ask questions and share resources, with moderation by AAFA staff. They will be able to send a "group private message" that includes the subject, the AAFA staff providing navigation support, and the AAFA administrator. Subjects will then communicate with AAFA staff about insurance issues, access to asthma care, and assistance with asthma costs. Messages are referred

Figure 1: Study flow

to trained AAFA staff who respond by the next business day—and usually within the same day— with answers, referrals, or other follow-up. AAFA's online community is staffed with trained community engagement managers during "normal" business hours as well as nights and weekends in order to be available for patients when they need support. For subjects in this study, AAFA staff will offer telephonic follow-up as needed to help identify available insurance options and eligibility criteria and suggest important insurance plan attributes and cost management strategies to consider.

Data collection

One month after receiving the intervention, subjects will be emailed a RedCap link to a follow-up survey to measure changes in insurance coverage and other outcomes. The follow-up survey will be structured similarly to the baseline survey, with closed-ended questions about insurance coverage, asthma care and control, health care access and affordability. For intervention subjects, the follow-up survey will also ask closed and open-ended questions about implementation outcomes such as uptake, acceptability, feasibility, usability, and fidelity. The survey will be designed to be completed in an average of 20 minutes and we will offer a \$20 gift card for completion.

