Patient stakeholders from the AFFORD Patient Family Advisory Council will provide input on interpretation of study findings in the context of their lived experience, and will provide input on strategies for dissemination to key stakeholders (PC-1, PC-4).

Limitations

Our study subjects will be recruited from the AAFA community, so generalizability may be limited. Those who participate in the AAFA community may not be representative of the national population of patients with asthma. Among those eligible, we will oversample racial/ethnic minority participants to ensure a more diverse sample. As this is a pilot study, efficacy testing will be limited but we expect to have a large enough sample size to detect moderate to large differences in coverage. Given the pilot nature of the study, we will not be able to measure longer-term health and well-being outcomes. Survey outcome measures may be subject to recall bias, but the use of a one-month survey will allow a shorter timeframe for participants to recall.

Timeline

TIMELINE	Year 1											Yea	r 2				
Activity	Jul-20	Se	p-20	Nov	-20	Jan	-21	Mar	-21	May	-21	Jul-	21	Sep	-21	Nov	-21
Aim 1																	
IRB approval																	
Train navigators on study protocol, pretest intervention																	
Recruit study sample through AAFA																	
Field baseline survey																	
Provide intervention																	
Field follow-up surveys					1-mon	th		4-mont	h								
Analyze follow-up survey data							1-n	nonth		4-m	onth						
Presentations, manuscripts									1-m	nonth		4-m	onth				
Aim 2																	
Conduct interviews																	
Analyze interview data																	
Presentations, manuscripts																	

References

- CDC Covid-19 Response Team. Preliminary estimates of the prevalence of selected underlying health conditions among patients with Coronavirus Disease 2019 - United States, February 12-March 28, 2020. MMWR Morbidity and mortality weekly report. 2020;69(13):382-386.

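### The secondary financial-burden outcome can count burden carried over from before entry in both arms, which shrinks the difference between them; the plan states no period starting at randomisation

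*Combined protocol and SAP*

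**What the plan says.** The Outcomes section of Aim 1 has two secondary outcomes: taking less asthma medication than prescribed because of cost, and "whether they experienced health care-related financial burden". The components of the second include "problems paying medical bills and/or paying off medical bills over time, having to set up a payment plan with a doctor or hospital", together with difficulty meeting basic household bills because of medical costs. No component is limited to bills or events after entry, and neither outcome has a stated reference period.

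Eligibility (Participants) requires that the person "lost employer-sponsored health insurance after February 2020". No maximum gap between losing coverage and joining the trial is given.

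On measurement, the baseline survey covers "current access and cost challenges" (Design). Data collection says of the one-month survey: "The follow-up survey will be structured similarly to the baseline survey". The later survey ("Four months later, intervention and control subjects will be emailed a RedCap link") is similar and is meant to "measure changes in insurance coverage, asthma care and control, health care access, and affordability".

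The Analysis Plan compares unadjusted outcomes by chi-square or t test and adjusts only for covariates that turn out unbalanced. Baseline burden is not among the covariates it names. The only remark on recall time is in Limitations: "the use of a one-month survey will allow a shorter timeframe for participants to recall".

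**The concern.** Gradual repayment of a bill and a payment plan already in place are lasting states. A participant who lost coverage months before joining, ran up bills and is still repaying them meets the stated definition at one and four months, even if nothing new has happened since entry. Any new burden in that person, or any avoidance of it, cannot alter a response that is already positive on the composite.

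Medication under-use has a related but weaker problem. It is not a debt that persists, but without a stated start its recall window may reach back before entry.

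What is at stake is sensitivity. Background positives common to both arms shrink the contrast, whether the true effect is a benefit or a harm such as costly new coverage. The Overview of Aim 1 also says that effect sizes from this pilot will be used to power a larger trial, so a shrunken burden effect could carry into that planning.

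**Working it through.** **What the plan supplies.** The Analysis Plan expects 100 intervention and 200 control participants with follow-up data after 30% loss. This agrees with the randomised numbers: 145 × 0.70 = 101.5 and 285 × 0.70 = 199.5. The stated 80% power concerns uninsurance. No rate, effect size or power is given for financial burden, so there is no burden figure to reproduce. All burden rates below are assumptions.

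**Model.** Let c be the share of each arm that meets the definition at follow-up through carried-over burden, whatever happens after entry. Let p_C and p_I be the rates of new burden in control and intervention, taken to be the same in people with and without carried-over burden. Then

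- observed rate = c + (1 − c) × p
- observed difference = (1 − c) × (p_C − p_I)

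For a 10-point difference in new burden: c = 20% gives 0.8 × 10 = 8 points, c = 40% gives 6, and c = 60% gives 4.

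**Effect on power.** Two-sided alpha 0.05, 100 vs 200, normal approximation with pooled variance under the null. For example, with 30% vs 15% and c = 20%:

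- observed rates: 0.20 + 0.80 × 0.30 = 0.44 and 0.20 + 0.80 × 0.15 = 0.32; difference 0.12
- pooled rate: (200 × 0.44 + 100 × 0.32)/300 = 0.40
- null standard error: √(0.40 × 0.60 × (1/100 + 1/200)) = 0.0600
- alternative standard error: √(0.32 × 0.68/100 + 0.44 × 0.56/200) = 0.0584
- power: Φ((0.12 − 1.96 × 0.0600)/0.0584) = Φ(0.04) = 52%

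| c | 30% vs 15%: difference, power | 20% vs 10%: difference, power |
|---|---|---|
| 0 | 15.0 points, 83% | 10.0 points, 60% |
| 10% | 13.5, 66% | 9.0, 39% |
| 20% | 12.0, 52% | 8.0, 28% |
| 30% | 10.5, 40% | 7.0, 21% |
| 50% | 7.5, 25% | 5.0, 13% |

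**If carried-over burden can respond.** Let Δ be the effect in people without carried-over burden and Δ_c the effect in those with it. The observed difference is (1 − c)Δ + cΔ_c. With Δ = 10 and c = 40%: Δ_c = 0 gives 6 points, Δ_c = 5 gives 0.6 × 10 + 0.4 × 5 = 8, and Δ_c = 10 gives 10, which is no shrinkage.

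**Look-back.** If an item asks about the past W months and the survey falls t months after entry, the share of the window before entry is (W − t)/W, or zero if W ≤ t. W is not in the documents, and I take the later survey as four months after entry.

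| W (months) | t = 1 | t = 4 |
|---|---|---|
| 4 or less | up to 3/4 = 75% | 0% |
| 6 | 5/6 = 83% | 2/6 = 33% |
| 12 | 11/12 = 92% | 8/12 = 67% |

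**The case against.** The strongest reply is that the documents do not contain the questionnaire. Outcomes says the items include validated measures and items from earlier surveys, and these may carry reference periods. The baseline survey's emphasis on current difficulties points away from a long look-back, and any window of four months or less leaves nothing before entry at the four-month survey. This stands: what can be shown is that the plan states no period, not that the instrument lacks one. It does not settle the matter, because a short look-back does not remove old debt still being repaid.

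Second, a reader might infer that earlier debts are beyond the intervention's reach. The documents do not support that. The Intervention section describes help with the cost of asthma care, so existing difficulty in paying medical or household bills could ease. Relief of existing burden is a legitimate target, which is a reason to measure it separately and not to discard it. The full (1 − c) shrinkage applies only to burden that does not move.

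Third, the plan has safeguards: randomisation, affordability measured at baseline, and follow-up surveys described as measuring change. Randomisation balances old debt in expectation. But the stated analysis compares unadjusted outcomes, and nothing says how the baseline burden response enters it.

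Finally, a reader might take the recall remark in Limitations as a claimed cure for four-month recall. It says only that the one-month survey shortens recall, and needs no rewording.

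**Conclusion.** The point holds as a loss of sensitivity in a secondary outcome. The stated definition admits lasting states, entrants may have lost coverage at any time after February 2020, no period starts at randomisation, and the comparison is unadjusted. Burden carried over from before entry therefore counts in both arms.

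The size cannot be fixed from the documents. The (1 − c) factor assumes that carried-over burden does not respond to the intervention and that new burden is equally common, and equally responsive, in those who carry it. In the 30% vs 15% illustration, c = 30% takes power from 83% to 40%. With c near zero, or carried-over burden that responds as well as new burden, little or nothing is lost.

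A reader might infer that the outcome is biased in favour of one arm. It is not: old debt is balanced in expectation and the pull is towards no difference, for benefit and harm alike. The primary coverage outcome is unaffected, and the plan itself calls efficacy testing in this pilot limited.

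**What to change.** In both follow-up surveys, ask the medication under-use and burden items for the period since the participant's baseline survey, with that date filled in by REDCap. Design places the baseline survey after randomisation, and Intervention places it before the intervention is offered, so it is a usable start. The anchor should be the baseline date and not the previous survey: otherwise the four-month outcome would miss burden arising in the first month, and people who skipped the one-month survey would have a longer window than others.

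Ask separately whether bills or payment plans are new since that date or continue from before. Keep the original current-burden item, so that relief of existing burden stays visible, and report new and ongoing burden side by side. State in the Analysis Plan that the burden comparison adjusts for the baseline burden response, whether or not it looks unbalanced.

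The cost is one or two extra items, a slight departure from source wording, reliance on respondents to date their bills, and a lower event rate for new-onset burden than for any burden. Sample size and survey schedule do not change. The wording must be settled before the surveys go out, because undated answers cannot be reliably separated later; the baseline adjustment can be pre-specified even if some surveys have already been sent.
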